4.1 Subject Disposition

A subject disposition table will be presented that displays the number of subjects enrolled in addition to the number and percentage of subjects (based on the number of randomized subjects) randomized, treated, completed, and discontinued. This table will also contain counts for each reason for premature study discontinuation. Furthermore a listing of reasons for early study discontinuation will also be provided.

The number of subjects within each of the analysis sets used in the study will be given. The reasons for exclusion from each set will be listed.

Finally, an accountability table as in Table F.1 in Appendix F of ANSI Z80.11-2012 will be provided.

4.2 Background and Demographic Characteristics

Background and demographic characteristics will be summarized on the subject-level version of the ITT and Safety Analysis Sets (i.e. the subject must have at least one eye for which treatment has begun) by surgery group and overall. The number and percentage of subjects will be presented for the categorical variables and descriptive statistics for the continuous variables.

Demographics

Categorical variables

- age (years) (<65, ≥65)
- sex (Female, Male, Unknown, Undifferentiated)
- ethnicity (Hispanic or Latino, Not Hispanic or Latino, Not Reported, Unknown)
- race (White, Black or African American, American Indian or Alaska Native, Asian, Native Hawaiian or Other Pacific Islander, Other)

Continuous variable

- age (years)

Ocular characteristics

Categorical variables

- curvature (D) (for K1/Flat, K2/Steep)
- meridian (degrees) (for K1/Flat, K2/Steep)

Continuous variable

- axial length (mm) (for each eye)
- corneal thickness (µm) (for each eye)
- pupil size (mm) (for each eye)

4.3 Medical History

Medical history data will be listed by surgery group for all randomized subjects.

4.4 Prior and Concomitant Medications

Prior medications will be defined as drugs taken and stopped prior to surgery. Any medication given at least once between surgery and the last day of study visit will be a concomitant medication, including those which were started pre-surgery and continued into the post-surgery period.

Prior or concomitant medication will be identified based on recorded start dates of medication taking. Medications will be identified by anatomical therapeutic classification (ATC) according to the World Health Organization (WHO) Drug Reference List dictionary (201603 or a more recent version).

Prior and concomitant medications will be listed by surgery group for all randomized subjects.

5 Effectiveness Analysis Strategy

[figure not shown]
5.1 Effectiveness Endpoints

[figure not shown]
Primary Endpoint

- Percentage of eyes with manifest refraction cylinder ≤ 0.5 D at 3 months.

Secondary Endpoints

- Mean manifest refraction cylinder (D) at 3 months.
- Mean UCVA (logMAR) at 3 months.

5.2 Effectiveness Hypotheses

The primary effectiveness endpoint to be tested is that Topography Guided LASIK is superior to SMILE in the percentage of eyes with manifest refraction cylinder ≤ 0.5 D at 3 months (Month 3). The following null hypothesis will be tested at the two-sided 5% significance level ($\alpha=0.05$):

$$H_0: p_L = p_S$$

$$H_1: p_L \neq p_S$$

where p_L and p_S refer to the percentage of eyes with manifest refraction cylinder within (\leq) 0.5 D in the Topography Guided LASIK arm and SMILE arm, respectively.

The secondary effectiveness hypotheses to be tested are that:

- Topography Guided LASIK is superior to SMILE in mean manifest refraction cylinder at 3 months (Month 3).

- The following null hypothesis will be tested (two-sided):

$$H_0: \mu_L = \mu_S$$

$$H_1: \mu_L \neq \mu_S$$

where μ_L and μ_S denote the mean manifest refraction cylinder in the Topography Guided LASIK arm and SMILE arm, respectively.

- Topography Guided LASIK is superior to SMILE in mean UCVA at 3 months (Month 3).

- The following null hypothesis will be tested (two-sided):

$$H_0: \mu_L = \mu_S$$

$$H_1: \mu_L \neq \mu_S$$

where μ_L and μ_S denote the mean UCVA in the Topography Guided LASIK arm and SMILE arm, respectively.

5.3 Statistical Methods for Effectiveness Analyses

5.3.1 Primary Effectiveness Endpoint

The percentage of eyes with manifest refraction cylinder \leq 0.5 D at 3 months (Month 3) will be analyzed for the ITT Analysis Set using the chi-square test quoted in Fleiss et al (Fleiss 2003) based on the two-sided 5% significance level ($\alpha=0.05$). As the study surgery is bilateral, i.e. it is planned for both eyes for each subject to be treated on the day of surgery; the intracluster correlation/ agreement between eyes within subject will be taken into account.

Descriptive statistics at each visit will also be provided by surgery group for the percentage of eyes with manifest refraction cylinder \leq 0.5 D for the ITT Analysis Set.

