## 10 SUBJECT POPULATION

Subjects ≥ 18 years of age [subjects in Singapore must be 21 years of age or older and subjects in Korea must be upon completion of 19 years of age or older due to local regulations] with myopia requiring refractive error correction of -0.5 to -8.0 D optical infinity adjusted manifest sphere and astigmatism correction of -0.75 to -5.0 D manifest refraction cylinder and at least 0.75 D of corneal astigmatism in both eyes, and fulfilling all other eligibility criteria in Section 10.1 and Section 10.2, will be enrolled into the study.

Within a 45 calendar day window prior to surgery, subjects will be screened and randomized in a 1:1 manner to receive EX500 for Topography Guided LASIK or VisuMax for SMILE.

All ocular related inclusion and exclusion criteria apply to both eyes. It is estimated that approximately 6 months will be required to complete enrollment for this study.

*NOTE:* No one site will randomize more than 25% of the total subject cohort and enrolment will be competitive in order to complete enrolment on time.

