### 10.1 Inclusion Criteria

Below is a list of inclusion criteria. Ocular criteria must be met in both eyes.

- 1. Subjects 18 years of age or older at the time of informed consent [subjects in Singapore must be 21 years of age or older and subjects in Korea must be upon completion of 19 years of age or older due to local regulations]
- 2. Able to comprehend and sign an informed consent form (ICF).
- 3. Willing and able to complete all post-surgery visits.
- 4. Myopia requiring (a) refractive error correction of -0.5 to -8.0 D optical infinity adjusted manifest refraction sphere with (b) astigmatism correction of -0.75 to -5.0 D manifest refraction cylinder and (c) at least 0.75 D of corneal astigmatism.
- 5. Intended treatment is targeted for emmetropia.
- 6. Pre-surgery BCVA of 0 logarithm of the minimum angle of resolution (logMAR) (20/20) or better.

Alcon - Business Use Only Protocol - Clinical Effective Date: 19-Mar-2017
Page 47 of 81

Document: TDOC-0052425 Version: 2.0; Most-Recent; Effective; CURRENT

Status: Effective

7. Spherical equivalent difference of  $\leq 0.5$  D between the optical infinity adjusted manifest and optical infinity adjusted cycloplegic refraction outcomes.

- 8. Spherical equivalent difference of ≤ 0.5 D between refractive error corrections for a minimum of 12 months prior to surgery verified by consecutive optical infinity adjusted refractions and/or medical records or prescription history.
- 9. For contact lens wearers Spherical equivalent difference of ≤ 0.5 D between outcomes from consecutive optical infinity adjusted manifest refraction outcomes performed at least 7 days apart after the contact lens wear has been stopped for the appropriate period of time as follows:
  - Soft (extended and daily wear) = 3 days
  - Rigid Gas Permeable (RGP) or Toric = 2 weeks
  - Hard polymethyl methacrylate (PMMA) = 3 weeks

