### NOTES:

- Each subject must be refracted by an ophthalmologist, optometrist, or a skilled technician. For further details, refer to MOP.
- To ensure the stability of refraction, eligible subjects who currently wear contact lenses must discontinue their use for the appropriate amount of time before undergoing refractive laser surgery in the study as indicated in Table 12–1.

*NOTE*: A contact lens wearer is defined as someone who has worn contact lenses within 3 months prior to the Pre-Surgery Visit.

Table 12–1 Minimum time to stop wearing contact lens before Pre-Surgery Visit

Type of Contact Lens	Minimum Time to Stop Wearing Contact Lens before Pre-Surgery Visit
Hard (PMMA) lenses	3 weeks
RGP lenses	2 weeks
Soft (extended and daily wear)	3 days

- Perform lighting measurements for VA and contrast sensitivity testing.
- Measure distance UCVA in photopic conditions using an Early Treatment
  Diabetic Retinopathy Study (ETDRS) chart at 3 meters (10 feet) or 4 meters (13
  feet) recorded in logMAR. For subjects who cannot read English letters, a
  numerical, Tumbling E or a Landolt C logMAR chart can be used.
- Measure uncorrected contrast sensitivity in mesopic conditions using a Vector

Effective Date: 19-Mar-2017 Page 55 of 81 Alcon - Business Use Only Protocol - Clinical

Version: 2.0; Most-Recent; Effective; CURRENT Document: TDOC-0052425

Status: Effective

Vision Chart, recorded in logCS.

Measure manifest refraction at 4 meters and adjust for optical infinity.

- Measure distance BCVA in photopic conditions using Early Treatment ETDRS chart at 3 meters (10 feet) or 4 meters (13 feet) recorded in logMAR. For subjects who cannot read English letters, a numerical, Tumbling E or a Landolt C logMAR chart can be used.
- 7. Conduct the following procedures in an order that is feasible for your site:
  - Perform keratometry using a Topolyzer Vario.
  - Perform topography using a Topolyzer Vario. Verify that the corneal astigmatism is regular (bow-tie shape).
  - Perform pupillometry under mesopic conditions using an infrared pupilometer. The same instrument should be used throughout the study.
  - Perform axial length measurement using an optical biometer or any other instrument. The same instrument should be used throughout the study.
  - Perform pachymetry using an ultrasonic contact pachymeter device or any other instrument. The same instrument should be used throughout the study.

- 8. Perform slit lamp examination.

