### **Procedures related to laser surgeries:**

Laser systems and surgeries should be performed according to the Operator's (or User's) and Procedure's manuals. Refer to the manuals for specific instructions for device set up and

Effective Date: 19-Mar-2017 Page 57 of 81 Alcon - Business Use Only Protocol - Clinical

Version: 2.0; Most-Recent; Effective; CURRENT Document: TDOC-0052425

Status: Effective

maintenance to ensure proper function prior to treatment.

1. Ensure the Laser System is calibrated per manufacturer's instructions prior to the procedure.

- 2. Ensure that treatment parameters are precisely transferred from the files to the laser system.
  - *NOTE:* Treatment target is emmetropia for all eyes.
- 3. Perform surgery under topical anesthesia as per the normal routine of the surgeon.
  - *NOTE*: Although the surgery is planned to be bilateral, in the case where the Investigator decides to not perform the surgery on the second eye on the same day the first eye is treated, the Investigator may treat the second eye at a later date while the subject is still in the study. In this case, effectiveness and safety assessments will be conducted as per post-surgery follow up visits if the fellow eye is treated with the study treatment. If the fellow eye is not treated at all or treated with a non-study treatment, AEs will only be collected for this eye. Refer to the MOP Table 4-1 for further details.
- 4. Record any AEs and device deficiencies. Refer to Section 13 for further details. *NOTE:* SAEs must be entered into EDC within 24 hours of the Investigator's knowledge. OTHER NOTES:
- Record the method of flap creation for the Topography guided LASIK surgery (microkeratome blade or femtosecond laser) in source document.
- Record operating room temperature and environmental conditions control in source document.
- Record all surgical medications used during the procedure in source document.
- Record surgical problems or complications that occur during surgery in source document.
- Record any other procedures during surgery in source document.
- Record the surgeon who performed the surgery. No more than two surgeons per site should perform a type of surgery.

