# 15.4.1.2 Analysis Methods

The primary effectiveness analysis will be analyzed using the chi-square test quoted in Fleiss et al (Fleiss 2003) at the two-sided 5% significance level ( $\alpha$ =0.05). This statistic takes into account the intracluster correlation/ agreement between eyes within subject.

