1.3 Randomization

The randomization scheme will be generated and maintained by the Sponsor's (or designee) unmasked personnel who are not involved in the conduct or analysis of the study. Randomization will be implemented using Medidata Balance[®].

The randomization will be stratified by study site to ensure a balance of surgery allocations within each investigational site. Randomization will be in a 1:1 ratio.

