5.3.2 Secondary Effectiveness Endpoints

5.3.2.1 Manifest refraction

[figure not shown]
The mean manifest refraction cylinder at 3 months (Month 3) will be analyzed on eye level for the ITT Analysis Set using the statistic of Donner, et al (Donner 1981), which accounts for the intraclass correlation between eyes within subjects, based on the two-sided 5% significance level ($\alpha=0.05$).

[figure not shown]
Descriptive statistics at each visit will also be provided by surgery group for the mean manifest refraction cylinder for the ITT Analysis Set.

[figure not shown]

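### The main tests leave out site, the randomisation stratum, and baseline cylinder; adjusting for both costs little and could add about 0 to 3 points of power on the primary endpoint.

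*SAP*

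**What the plan says.** SAP 1.3 states: "The randomization will be stratified by study site to ensure a balance of surgery allocations within each investigational site". Protocol 7.2 likewise has 1:1 randomisation by investigational site.

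Baseline cylinder is available for every eye. Protocol 12.1.1 requires screening assessments in both eyes, including: "Measure manifest refraction at 4 meters and adjust for optical infinity". Protocol 10.1 admits manifest cylinder from -0.75 to -5.0 D.

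The primary endpoint is tested "using the chi-square test quoted in Fleiss et al (Fleiss 2003) based on the two-sided 5% significance level" (SAP 5.3.1). Protocol 15.4.1.2 describes what that test adjusts for: "This statistic takes into account the intracluster correlation/ agreement between eyes within subject". Mean cylinder and mean UCVA are both analysed "using the statistic of Donner, et al (Donner 1981), which accounts for the intraclass correlation between eyes within subjects" (SAP 5.3.2.1, with the same method in 5.3.2.2).

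The readable text names no site term, stratified test or baseline covariate for any of the three tests, and gives no reason for omitting them. Parts of the SAP effectiveness section are redacted, so this point concerns the main tests only, not supportive analyses that may be specified there.

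**The concern.** Two pieces of information that the trial will hold go unused.

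- **Site.** Stratification balances the arms within site. A test that ignores site still counts between-site variation in its standard error, so it is slightly conservative if success rates differ by site. Differences are plausible with about 8 sites across EMEA, Asia and LACAR, and with uneven recruitment: "No one site will randomize more than 25% of the total subject cohort and enrolment will be competitive".
- **Baseline cylinder.** Surgery corrects this quantity and the endpoint measures what remains of it. The permitted range is more than sixfold. If it predicts residual cylinder, any chance imbalance between arms passes straight into the unadjusted difference. The ITT set holds only eyes in which treatment began (SAP 3), and subjects can be excluded between randomisation and surgery (Protocol 9.2.1, 12.1.2), so balance among analysed eyes is not fully guaranteed by randomisation.

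At stake are some precision and some protection against imbalance, not the validity of the result.

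**Working it through.** **1. The plan's own figure.** Inputs from SAP 7: 90% vs 80% of eyes, intracluster correlation 0.39, two eyes per subject, two-sided 5%, 90% power.

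- Independent eyes per arm, pooled variance: [1.960·√(2·0.85·0.15) + 1.2816·√(0.9·0.1 + 0.8·0.2)]² / 0.10² = (0.990 + 0.641)² / 0.01 ≈ 266.
- Design effect: 1 + (2 − 1)·0.39 = 1.39.
- 266 × 1.39 = 369.7 eyes, or 184.9 subjects, hence 185 per arm.
- Power at 370/1.39 = 266.2 effective eyes per arm is 90.04%.

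The plan's figure reproduces, with no covariates involved.

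**2. Approximate gain on the primary endpoint.** Let R² be the share of outcome variance explained by site and baseline cylinder. Effective eyes become 266.2/(1 − R²). The documents give no R²; these values are assumptions.

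| R² | Power | Gain (points) |
|---|---|---|
| 0 | 90.0% | 0 |
| 0.02 | 90.6% | 0.6 |
| 0.05 | 91.4% | 1.4 |
| 0.10 | 92.8% | 2.8 |
| 0.15 | 94.1% | 4.0 |

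A gain of 0 to 3 points therefore corresponds to R² of about 0 to 10%.

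**3. Simulation.** 5000 trials per scenario, both analyses on the same data, 185 subjects per arm. Assumptions:

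- Eight sites of 92, 74, 56, 44, 37, 30, 22 and 15 subjects (total 370; 92/370 = 24.9%, just under the 25% cap), with permuted blocks of 4 within site.
- Baseline cylinder 0.75 D plus an exponential with mean 0.8 D, truncated at 5.0 D (SD 0.74 D, between-eye correlation 0.67).
- Logistic success model calibrated to 80%/90% and correlation 0.39.

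The adjusted analysis is an identity-link regression on treatment, site and cylinder with subject-clustered robust standard errors. Site SD is on the marginal logit scale. Cylinder strength is shown as success at 1 D vs 3 D, or as odds ratio (OR) per dioptre.

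| Scenario | Planned | Adjusted | Gain (points) |
|---|---|---|---|
| Neither prognostic | 0.905 | 0.904 | −0.1 |
| Site only, SD 0.3 | 0.913 | 0.917 | 0.4 |
| Site only, SD 0.8 | 0.913 | 0.928 | 1.5 |
| Cylinder only, 88% vs 77% | 0.906 | 0.912 | 0.6 |
| Cylinder only, 90% vs 70% | 0.911 | 0.928 | 1.7 |
| Cylinder only, 92% vs 62% | 0.912 | 0.944 | 3.2 |
| Both: OR 0.67, site SD 0.3 | 0.901 | 0.909 | 0.8 |
| Both: OR 0.50, site SD 0.5 | 0.912 | 0.932 | 2.0 |
| Both: OR 0.37, site SD 0.8 | 0.917 | 0.948 | 3.1 |

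The Monte Carlo SE of a power difference is 0.001 to 0.003. Under the null (85%/85%), rejection was 0.043–0.054 for the planned test and 0.050–0.055 for the adjusted model (Monte Carlo SE 0.003).

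The variance ratios for cylinder alone were 0.982, 0.940 and 0.879. As extra subjects per arm, 185 × (1/ratio − 1) = 3.4, 11.8 and 25.5. For site alone the ratio was about 1.00, because stratification already balances site; its gain comes only from a corrected standard error.

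A separate simulation with a latent-normal model (4000 trials per scenario, simulated correlation about 0.35) gave:

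- no effects: 90.9% planned vs 91.0% adjusted;
- modest effects: 91.2% vs 92.7%;
- strong effects: 91.4% vs 94.8%, and 91.7% vs 95.5%.

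Three points is therefore not a ceiling.

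**4. Chance imbalance.** With the cylinder distribution above, the SE of the between-arm difference in mean baseline cylinder is √[2 × 0.74² × (1 + 0.67)/2 / 185] = 0.070 D. The slopes are (88 − 77)/2 = 5.5 and (92 − 62)/2 = 15 points per dioptre. A one-SE imbalance then shifts the unadjusted difference by 0.4 to about 1.1 points, against an assumed effect of 10.

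**5. Secondary endpoints.** For mean cylinder the variance falls by about r², where r is the baseline-to-outcome correlation: 0.3² = 9% to 0.5² = 25%, with r assumed. The documents give no SD or effect size for the secondaries, so no power gain can be computed. None is claimed for UCVA.

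**The case against.** The strongest reply is that nothing is broken. The planned test is valid, meets its stated power and matches the sample-size calculation, which also uses no covariates. Every gain above zero rests on inputs that the documents do not supply, and the upper end needs success to fall from 92% at 1 D to 62% at 3 D. This stands: the gain is unknown and may be zero.

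Site adds little. That also stands. Its gain was 0.4 to 1.5 points, with no reduction in the true variance. Nor would a site term separate treatment from surgeon, since the limit applies per procedure: "No more than two surgeons per site should perform a type of surgery". Each arm at a site may have its own surgeons.

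The adjusted model's null rejection reached 0.055. That is (0.055 − 0.050)/0.003 ≈ 1.7 Monte Carlo SEs above nominal, so a small inflation cannot be ruled out.

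An identity link is not the only workable choice. At least one site had only successes in 2% to 22% of simulated trials. In a logistic model that makes the site's own intercept diverge but leaves the treatment effect estimable, and pooling or penalised likelihood would deal with it. The identity link is preferred because it gives the difference in percentages directly and avoids the problem.

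The adjusted model could instead be supportive, leaving the primary method alone. That would show the effect of an imbalance, but would add nothing to the power of the primary test.

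**Conclusion.** The concern holds as an efficiency and design-matching point. The readable main tests use neither the randomisation stratum nor the most obvious baseline covariate, and the documents give no reason. At 185 subjects per arm, adjustment loses essentially nothing if neither is prognostic. It adds roughly 1 to 2 points of power under modest to moderate assumed effects, and about 3 or slightly more under strong ones, mostly from baseline cylinder. These figures apply to the primary endpoint only and depend on the assumed prognostic strengths, site sizes and cylinder distribution. The change should be made because the downside is close to nil, but the trial does not fail without it. Confidence is medium, because the prognostic strengths are unknown.

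**What to change.** **Primary endpoint (Protocol 15.4.1.2, SAP 5.3.1).** Pre-specify as the main analysis a GEE with identity link, constant variance, independence working correlation and robust variance clustered on subject. Terms: treatment, site (fixed) and baseline manifest cylinder (linear, in dioptres). Report the treatment coefficient, which is the marginal difference in percentage of eyes, with its 95% CI. Keep the Fleiss chi-square as supportive. State a small-site rule in advance, for example merging sites with fewer than 5 subjects in either arm into one stratum per region.

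**Mean cylinder (SAP 5.3.2.1).** Use a subject-clustered linear model with the same terms.

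**UCVA (SAP 5.3.2.2).** Keep the planned test, or add the same terms only if they are judged prognostic in advance.

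**Cost and timing.** The cost is SAP wording, a short protocol amendment and some programming; no extra data or subjects. The SAP is still based on protocol Version 1.0 and needs re-issue for Version 2.0 in any case. Sponsor staff may know treatment assignment (SAP 1.4), so the change should be documented before anyone sees post-surgery outcomes by arm. Amendment 1 records 2 patients enrolled, when the risk of an apparently data-driven change was small; it grows with delay.

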5.3.2 Secondary Effectiveness Endpoints

5.3.2.1 Manifest refraction

[figure not shown]
The mean manifest refraction cylinder at 3 months (Month 3) will be analyzed on eye level for the ITT Analysis Set using the statistic of Donner, et al (Donner 1981), which accounts for the intraclass correlation between eyes within subjects, based on the two-sided 5% significance level ($\alpha=0.05$).

[figure not shown]
Descriptive statistics at each visit will also be provided by surgery group for the mean manifest refraction cylinder for the ITT Analysis Set.

[figure not shown]
